### 12.2 Reporting of adverse events

All events meeting the definition of an AE must be collected and reported. This includes events from the first trial-related activity after the subject has signed the informed consent until the end of the post-treatment follow-up period (V92). The events must be recorded in the applicable eCRF forms in a timely manner, see timelines below and [Figure 12-1](#).

During each contact with the trial site staff, the subject must be asked about AEs and technical complaints, for example by asking: “Have you experienced any problems since the last contact?”.

All AEs, observed either by the investigator or subject, must be reported by the investigator and evaluated.

All AEs must be recorded by the investigator on an AE form. The investigator should report the diagnosis, if available. If no diagnosis is available, the investigator should record each sign and symptom as individual AEs using separate AE forms.

For SAEs, a SIF must be completed in addition to the AE form. If several symptoms or diagnoses occur as part of the same clinical picture, one SIF can be used to describe all the SAEs.

For all non-serious AEs, the applicable forms should be signed when the event is resolved or at the end of the trial at the latest.

#### Timelines for initial reporting of AEs

The investigator must complete the following forms in the eCRF within the specified timelines:

- **SAEs:** The AE form **within 24 hours** and the SIF **within 5 calendar** days of the investigator’s first knowledge of the SAE. Both forms must be signed **within 7 calendar** days from the date the information was entered in the eCRF.
- **For SAEs requiring reporting on a specific event form:** In addition to the above the specific event form **within 14 calendar days** from the investigator’s first knowledge of the AE.

Protocol  
 Trial ID: NN1250-4300  
 UTN: U1111-1191-3018  
 EudraCT no.: 2017-000048-17

[figure not shown]
**CONFIDENTIAL**

Date: 17 December 2020  
 Version: 4.0  
 Status: Final  
 Page: 67 of 110

**Novo Nordisk**

- **Events for Adjudication:** The adjudication form should be completed **within 14 calendar days** of the investigator’s first knowledge of the AE, see Section 12.3. The investigator should provide copies of the source documentation preferably within 4 weeks of event identification.

If the eCRF is unavailable, the concerned AE information must be reported on a paper AE form and sent to Novo Nordisk by fax, email or courier within the same timelines as stated above. When the eCRF becomes available again, the investigator must enter the information on the form into the eCRF. Contact details (fax, telephone, email and address) are provided in the investigator trial master file.

Timelines are for the completion of forms from the time of investigator’s awareness AEs requiring specific event forms are described in Section 12.1.5 AEs for adjudication are described in Section 12.7.3

AE: Adverse event SIF: Safety information form

**Figure 12–1 Reporting of AEs.**

**Novo Nordisk assessment of AE expectedness**

Novo Nordisk assessment of expectedness is performed according to the current versions and any update of the IBs for IDeg, IDet and IAsp.

**Reporting of trial product-related SUSARs by Novo Nordisk**

Novo Nordisk will notify the investigator of trial product-related suspected unexpected serious adverse reactions (SUSARs) in accordance with local requirements and ICH GCP. In addition, the investigator will be informed of any trial-related SAEs that may warrant a change in any trial procedure.

In accordance with regulatory requirements, Novo Nordisk will inform the regulatory authorities, including the European Medicines Agency (EMA), of trial product-related SUSARs. In addition, Novo Nordisk will inform the IRBs/IECs of trial product-related SUSARs in accordance with local requirement and ICH GCP, unless locally this is an obligation of the investigator.

Protocol  
Trial ID: NN1250-4300  
UTN: U1111-1191-3018  
EudraCT no.: 2017-000048-17

~~CONFIDENTIAL~~

Date: 17 December 2020  
Version: 4.0  
Status: Final  
Page: 68 of 110

Novo Nordisk

### Novo Nordisk products used as concomitant medication

If an AE is considered to have a causal relationship with a Novo Nordisk marketed product used as concomitant medication in the trial, it is important that the suspected relationship is reported to Novo Nordisk, e.g. in the alternative aetiology section on the safety information form. Novo Nordisk may need to report this adverse event to relevant regulatory authorities.

### 12.3 Follow-up of adverse events

The investigator must record follow-up information by updating the forms in the eCRF.

Follow-up information must be reported to Novo Nordisk according to the following:

- **SAEs:** All SAEs must be followed until the outcome of the event is “recovered/resolved”, “recovered/resolved with sequelae” or “fatal”, and until all queries have been resolved. Cases of chronic conditions, cancer or AEs ongoing at time of death (where death is due to another AE) may be closed with the outcome “recovering/resolving” or “not recovered/not resolved”. Cases can be closed with the outcome of “recovering/resolving” when the subject has completed the follow-up period and is expected by the investigator to recover.  
The SAE follow-up information should only include new (e.g. corrections or additional) information and must be reported **within 24 hours** of the investigator’s first knowledge of the information. This is also the case for previously non-serious AEs which subsequently become SAEs.
- **Non-serious AEs:** Non-serious AEs must be followed until the outcome of the event is “recovering/resolving”, “recovered/resolved” or “recovered/resolved with sequelae” or until the end of the follow-up period stated in the protocol, whichever comes first, and until all queries related to these AEs have been resolved. Cases of chronic conditions, cancer or AEs ongoing at time of death (where death is due to another AE) may be closed with the outcome “recovering/resolving” or “not recovered/not resolved”. Cases can be closed with the outcome of “recovering/resolving” when the subject has completed the follow-up period and is expected by the investigator to recover.

The investigator must ensure that the recording of the worst case severity and seriousness of an event is kept throughout the trial. A worsening of an unresolved AE must be reported as follow up with re-assessment of severity and/or seriousness of the event.

Queries or follow-up requests from Novo Nordisk must be responded to **within 14 calendar days** from the date of receipt of the request, unless otherwise specified in the follow-up request.

**SAEs after end of trial:** If the investigator becomes aware of an SAE with a suspected causal relationship to the investigational medicinal product occurring to a subject after the subject has

Protocol  
Trial ID: NN1250-4300  
UTN: U1111-1191-3018  
EudraCT no.: 2017-000048-17

CONFIDENTIAL

Date: 17 December 2020  
Version: 4.0  
Status: Final  
Page: 69 of 110

Novo Nordisk

ended the trial, the investigator should report this SAE within the same timelines as for SAEs during the trial.

## 12.4 Technical complaints and technical complaint samples

### 12.4.1 Reporting of technical complaints

All technical complaints on any of the following products:

- Insulin degludec (IDeg), 100 U/mL, 3 mL PDS290 pen injector (FlexTouch®)
- Insulin detemir (IDet), 100U/mL, 3 mL pre-filled pen (FlexPen®)
- Insulin aspart (IAsp), 100 U/mL, 3 mL pre-filled pen (FlexPen®)
- Novo Nordisk needles for pen devices

which occur from the time of first usage of the product until the time of the last usage of the product, must be collected and reported to Customer Complaint Center, Novo Nordisk.

Contact details (fax, email and address) are provided in [Attachment I](#) to the protocol.

The investigator must assess whether the technical complaint is related to any AEs and/or SAEs.

Technical complaints must be reported on a separate technical complaint form:

- One technical complaint form must be completed for each affected DUN
- If DUN is not available, a technical complaint form for each batch or lot number must be completed

The investigator must complete the technical complaint form in the eCRF within the following timelines of the trial site obtaining knowledge of the technical complaint:

- Technical complaint assessed as related to an SAE **within 24 hours**
- All other technical complaints **within 5 calendar days**

If the eCRF is unavailable or when reporting a technical complaint that is not subject related, the information must be provided on a paper form by fax, email or courier to Customer Complaint Center, Novo Nordisk, within the same timelines as stated above. When the eCRF becomes available again, the investigator must enter the information on the technical complaint form in the eCRF.

### 12.4.2 Collection, storage and shipment of technical complaint samples

The investigator must collect the technical complaint sample and notify the monitor **within 5 calendar days** of obtaining the sample at trial site. The monitor must coordinate the shipment to Customer Complaint Center, Novo Nordisk (the address is provided in [Attachment I](#)) and ensure that the sample is sent as soon as possible. A copy of the technical complaint form must be included

Protocol  
Trial ID: NN1250-4300  
UTN: U1111-1191-3018  
EudraCT no.: 2017-000048-17

CONFIDENTIAL

Date: 17 December 2020  
Version: 4.0  
Status: Final  
Page: 70 of 110

Novo Nordisk

in the shipment of the sample. If several samples are returned in one shipment, the individual sample and the corresponding technical complaint form must be clearly separated.

The investigator must ensure that the technical complaint sample contains the batch or lot number and, if available, the DUN. All parts of the DUN should be returned.

If the technical complaint sample is unobtainable, the investigator must specify on the technical complaint form why it is unobtainable.

Storage of the technical complaint sample must be done in accordance with the conditions described for the product.

### 12.5 Adverse events related to pregnancies

The investigator must report information about the pregnancy, pregnancy outcome, and health of the newborn infant(s), as well as AEs in connection with the pregnancy and AEs in the foetus and newborn infant(s) until 2 months of age in the eCRF.

#### Standard local practice for treatment/procedures during pregnancy

Treatment or procedures of mother and/or foetus/infant(s) that are standard local practice and/or done for prophylactic purposes do not constitute AEs. Examples could be prophylactic i.v. glucose given to a newborn infant of a diabetic mother or prophylactic antibiotic treatment of a newborn infant due to an infection in the mother. The infection should, however, be reported as AE in the mother.

#### Terms not to be used for reporting

The diagnosis and symptoms used for reporting should always describe the condition as specific as possible. Unspecific diagnoses such as “diabetic foetopathy” should not be used. Instead the specific diagnose and/or symptom(s) under this term should be reported as individual AEs.

#### Preterm delivery

Preterm delivery where the outcome of the delivery is without complications should not be reported as an AE in itself, neither on mother or infant.

#### Pregnant subjects who withdraw consent

For pregnant subjects who withdraw consent, efforts should be made to obtain information related to the pregnancy and pregnancy outcome. Information about the pregnancy and pregnancy outcome/health of the newborn infant(s) must be reported on the **paper pregnancy forms** Maternal Form 1A and 1B, respectively. In case of an abnormal pregnancy outcome, further information must be reported on the Maternal Form 2. In addition, information from the biological father (if

Protocol  
Trial ID: NN1250-4300  
UTN: U1111-1191-3018  
EudraCT no.: 2017-000048-17

~~CONFIDENTIAL~~

Date: 17 December 2020  
Version: 4.0  
Status: Final  
Page: 71 of 110

Novo Nordisk

known) must be reported on the Paternal Form, after an informed consent has been obtained, Section [18.2.1](#).

Initial reporting and follow-up information must be reported **within 14 calendar days** of the investigator's first knowledge of initial or follow-up information. Reporting timelines for AEs in connection with the pregnancy as well as in the foetus and newborn infant(s) are defined in Section [12.2](#).

The paper forms must be forwarded to Novo Nordisk either by fax, email or courier. Contact details are provided in [Attachment II](#) to the protocol.

### 12.5.1 Reporting adverse events in connection with the pregnancy

The investigator has to report relevant AEs in connection with the pregnancy. The forms and timelines for reporting AEs are defined in Section [12.2](#).

Pregnancy-related symptoms considered "normal" for a pregnant subject should only be reported as SAEs if they fulfil the seriousness criteria. Examples could be:

- Nausea
- Vomiting
- Skin itching
- Vaginitis
- Back pain
- Breast tenderness
- Hot flushes
- Swollen ankles or fingers

### 12.5.2 Reporting adverse events on foetus and/or infant(s)

The investigator has to report relevant AEs in the foetus and newborn infant(s). The SAEs that must be reported include abnormal outcome, such as foetal death (including spontaneous or induced abortion), and congenital anomaly(-ies) (including those observed at gross examination or during autopsy of the foetus), as well as other pregnancy complications fulfilling the criteria of an SAE.

Adverse events pertaining to the foetus/infant must be reported with the foetus/infant as the subject of the AE. The forms and timelines for reporting AEs are defined in Sections [12.2](#) and [12.7.3](#).

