#### Supportive pregnancy outcome endpoints

- Birth weight (kg)
- Pre-term delivery (delivery < 37 completed GWs) (yes/no)
- Early foetal death (delivery < 20 completed GWs) (yes/no)
- Perinatal mortality (death of foetus/infant between  $\geq 20$  completed GWs before delivery and < 7 completed days after delivery) (yes/no)
- Neonatal mortality (death of infant between  $\geq 7$  completed days after delivery and < 28 completed days after delivery) (yes/no)
- Presence of major abnormalities (classified according to EUROCAT) (yes/no)
- Live born infants (yes/no)
- Number of adverse events in the infant from delivery to final follow-up
- Neonatal hypoglycaemic episodes defined as plasma glucose  $\leq 1.7$  mmol/L (31 mg/dL) during the first 24 hours after birth or  $\leq 2.5$  mmol/L (45 mg/dL) between 24 hours and 48 hours after birth (yes/no)

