**Novo Nordisk**

### **Infant health information collected**

The following information will be collected for the infant:

- Details on the pregnancy outcome including:
  - Birth date
  - Gender
  - Gestational age (completed gestational weeks and days)
  - Head circumference of the newborna
  - Length of the newborna
  - APGAR scores assessed at 1 minute and 5 minutes after birth

a Measured in centimetres (cm) to one decimal place

- Standard Deviation (SD) score for birth weight (measured in grams (g) according to local normal curves for gestational age and sex) including the birth weight percentile.
- Details on the infant health status, including if the infant has any congenital anomaly or birth injury observed at gross examination or events such as induced abortion, resuscitation, respiratory distress syndrome (RDS), moderate or severe neonatal asphyxia, early foetal death or neonatal or perinatal death must be reported in the eCRF and as an SAE as per Section [12.5.2](#).
- To measure umbilical cord IDeg levels a cord blood sample should be drawn from the umbilical cord (applicable for subjects randomised to IDeg only). The sample should be collected at birth immediately after the umbilical cord has been cut.
- Umbilical cord pH (as part of standard of care).
- Postpartum neonatal plasma glucose and neonatal hypoglycaemia as defined in Section [8.5.16.4](#).
- Treatment given to the infant, e.g. with surfactant, ventilator or continuous positive airway pressure (CPAP).

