### Reporting of foetal or neonatal death

Foetal or neonatal death as a result of induced abortion should not be reported as an AE, except in situations where the foetus/neonate was deceased prior to the induced abortion.

In case of foetal or neonatal death the following applies:

- In case of foetal or neonatal death e.g. due to spontaneous abortion, ectopic pregnancy or stillbirth, an SAE must be reported with the mother as the subject of the AE.
- In case the foetus/neonate also has a diagnosis e.g. an anomaly, an additional SAE must be reported with the foetus/neonate as the subject of the AE.

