### Induced abortions

Induced abortion should not be reported as an AE as it is considered a procedure. Causes of induced abortions should always be reported as SAEs on either mother or foetus, as applicable.

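### Protocol 8.4.2 and 12.5.2 give opposing instructions on reporting induced abortion as an SAE and on the subject of a foetal or neonatal death, and the SAP settles neither

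*Protocol*

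**What the plan says.** **Induced abortion, instructions to report.** The opening paragraph of Protocol 12.5.2 puts "foetal death (including spontaneous or induced abortion") among the SAEs that must be reported. In Protocol 8.4.2, the list of infant health information includes "events such as induced abortion, resuscitation, respiratory distress syndrome (RDS") and further items, and says that these "must be reported in the eCRF and as an SAE as per Section" 12.5.2.

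**Induced abortion, instructions not to report.** One later subsection of 12.5.2, on deaths, says: "Foetal or neonatal death as a result of induced abortion should not be reported as an AE, except in situations where" (that is, unless death had preceded the procedure). Under the 12.5.2 subheading on induced abortions: "Induced abortion should not be reported as an AE as it is considered a procedure". That subsection adds that the cause is always an SAE, on mother or foetus as applicable.

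**Subject of the event.** The opening of 12.5.2 makes the foetus or infant the subject of any event that concerns it. The subsection on foetal or neonatal death says that in such a case "an SAE must be reported with the mother as the subject of the AE". It adds an SAE on the foetus or neonate only when there is also a diagnosis, such as an anomaly.

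**Endpoints that use these data.** Protocol 4.4 lists the number of infant adverse events from delivery to final follow-up, and "Early foetal death (delivery < 20 completed GWs) (yes/no"). The SAP (5.4.3) starts the infant AE window one calendar day before delivery and tabulates infant AEs and SAEs by arm. Its list of changes to the protocol analyses (6.2) mentions neither conflict.

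**The concern.** Pregnancy outcome is one of the two secondary objectives, and serious foetal and infant events will be few. If a site can count the same event as an SAE or not, or enter it under mother or infant, the tabulated numbers depend partly on which paragraph the site read.

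The cross-reference does not help. Section 8.4.2 sends the reader to 12.5.2, where both rules sit. More than a tally is affected: an SAE starts the 24-hour clock in 12.2. The opening of 12.5.2 also treats foetal death, with induced abortion inside it, as an abnormal outcome, and the next subsection sends abnormal outcomes to adjudication.

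The question of subject matters because a neonatal death filed only under the mother leaves the table where a reader would look for it. It may also miss the maternal endpoint. The pregnancy period ends on the delivery date (Protocol 17.2) and maternal events are assigned by onset (17.4.2.2). A death with later onset would then appear only in the post-pregnancy and in-trial maternal summaries.

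**Working it through.** The plan gives no figure to reproduce, so the check is to apply each instruction to the same case.

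**SAEs from one induced abortion of a living foetus**

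| Case | 8.4.2 and opening of 12.5.2 | Later subsections of 12.5.2 |
|---|---|---|
| No reportable cause | 1 | 0 |
| Reportable cause | 1 + 1 = 2 (abortion and cause) | 1 (cause only) |

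The difference is one SAE per case in both rows. The second row takes the instruction on causes to apply under either reading, since nothing contradicts it. Where the foetus had already died, the exception makes the death reportable, so there is no conflict over whether to report.

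**SAEs from one neonatal death with no separate diagnosis**

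| Rule followed | Infant SAEs | Maternal SAEs |
|---|---|---|
| Opening of 12.5.2 | 1 | 0 |
| Subsection on foetal or neonatal death | 0 | 1 |

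If the infant also has a diagnosis, the second rule adds an infant SAE and the infant table is not empty.

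**Route into the infant table.** The glossary counts termination of pregnancy as a delivery, and the SAP window opens one day before delivery. A foetal SAE dated to a termination can therefore fall inside the infant AE window.

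**Size per case.** SAP 6.3.1.1 gives 188 women in the full analysis set for pregnant women. Assuming an equal split and one foetus per woman:

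- 188 / 2 = 94 per arm, and 1 / 94 = 1.1 percentage points.
- With the planned 178 (Protocol 17.1), 178 / 2 = 89, and 1 / 89 = 1.1 percentage points.

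**Total size.** This would be the per-case shift multiplied by the number of terminations and of neonatal deaths without a diagnosis. The documents give neither number, so no total is offered.

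**Early foetal death.** Three texts have to be read together:

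- The parenthesis in Protocol 4.4 and 17.4.2.3, and in SAP 5.4.3, refers to delivery before 20 completed weeks. With the glossary entry for delivery, that could admit a termination.
- The glossary defines early foetal death itself as the death of a foetus before 20 completed weeks, and lists foetal death and termination as separate pregnancy outcomes.
- The opening of 12.5.2 puts induced abortion inside foetal death.

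The glossary favours leaving terminations out, but the endpoint wording does not say so.

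**The case against.** The best reply is that the specific instruction governs the general one. The subsection on induced abortions is written for this event and requires the cause as an SAE. The SAE definition (12.1.2), the abnormal-outcome paragraph of 12.5.2 and the adjudication table (Table 12–2) all name spontaneous abortion only, which fits that subsection. On this view the outliers are one parenthesis and one list item. Similarly, the subsection on deaths could be a deliberate exception to the general rule on subject, and its examples are all losses before or at birth.

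This shows which reading is more coherent. It does not remove two instructions that say an SAE must be reported, and no text gives one paragraph precedence. The examples are pregnancy losses, but the sentence covers neonatal death by name.

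It is also fair to say that deaths are not lost. The perinatal and neonatal mortality endpoints, the pregnancy outcome form and adjudication of all foetal and infant deaths (Tables 12–1 and 12–2) capture them. That stands, and it confines the problem to AE and SAE counts by subject. These outcomes are summarised without a formal test, which also limits the consequence.

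A reader might infer that elective terminations are counted as early foetal deaths. The documents do not support that as a firm statement, because the glossary defines the term by foetal death and keeps termination apart. A reader might also infer that the comparison between arms is unreliable because the trial is open-label. The same text applies to both arms, and nothing in the documents shows that sites would choose paragraphs differently by arm.

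**Conclusion.** The contradiction on induced abortion is real and stands in the current protocol. It moves the SAE count by one per termination of a living foetus. The rules on subject also conflict, and under one of them a neonatal death without a separate diagnosis is missing from the infant AE and SAE summaries. Each case is worth about 1.1 percentage points in an arm, assuming 94 women per arm and one foetus each.

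A reader might try to size the whole effect against the plan's allowance for delivery before GW 16 (0.10 × 178 = 18 women). That does not work. The 10% is an upper bound, it applies to GW 16 rather than 20 weeks, and no termination rate is given to set against it.

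This is an internal inconsistency worth correcting. It affects how safety counts are filed and leaves the primary analysis untouched.

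**What to change.** 1. Reconcile Protocol 8.4.2 and the opening of 12.5.2 with the two later subsections, so that one rule says whether an induced abortion is itself an SAE, who is its subject and how its cause is reported. The SAP already counts the 188 women in the past tense. If an amendment would come too late, state the rule in SAP 6.2 and apply it to existing cases.
2. Add one line to SAP 5.4.3: the death of a live-born infant filed under the mother is also counted in the infant AE and SAE tables.
3. Align the wording of the early foetal death endpoint in Protocol 4.4 and 17.4.2.3 and SAP 5.4.3 with the glossary definition, and tabulate terminations separately by arm from the pregnancy outcome form.

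The cost is a small amount of reclassification, using data already collected, and one extra table row.
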